8.3 Other study parameters

Descriptive statistics are calculated for covariates (smoking, sociodemographics and clinical data). The population characteristics of the subjects will be shown as averages or percentages (\pm standard deviation).

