6.1.3 Other study parameters (if applicable)

Exercise adherence:

Session attendance and compliance to the prescribed intensity, frequency and duration of exercises is monitored in exercise logs registered by the physical therapist. Patients in the exercise group are asked to keep an exercise log to register home-based exercise.

Demographic and clinical covariates

Information on smoking, alcohol intake, sociodemographic characteristics (e.g. age, ethnicity, education level, marital status), and exercise history will be obtained at baseline.

Clinical data:

- tumor characteristics (TNM-classification, degree of differentiation, hormone and Her2 receptor status)
- disease, treatment and treatment-related toxicity
- hospitalization
- performance status (ECOG)
- comorbidities (Charlson comorbidity index) and co-medication

Contamination is assessed from the control group at follow-up by a 3-item questionnaire, whether they changed their physical activity behavior and participated in structured exercise.

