6.2 Randomisation, blinding and treatment allocation

After baseline assessment, patients will be randomized into the exercise or the control group by the use of a computerized random generator. Randomization is stratified for TNBC (yes/no), extent of disease (N+/N-) and treatment (regular versus dose-dense).

The researcher that examines the physical fitness will not be blinded to group allocation.

The pathologist and analyst that will examine the blood and biopsy tissue will be blinded to group allocation.

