7.2 AEs, SAEs and SUSARs

7.2.1 Adverse events (AEs)

Adverse events are defined as any undesirable experience occurring to a subject during the study, whether or not considered related to the experimental intervention. For this study, all exercise-related AE's and AE's related to the biopsy (T1) and blood sampling (T0 en T1) reported spontaneously by the subject or observed by the investigator or his staff will be recorded.

In case a subject (with 3-weekly AC chemotherapy cycles) receives a prescription for G-CSF (pegfilgrastim) prior to the second cycle of chemotherapy (in case of neutropenia) this

will be reported by the coordinating researcher, because this might interfere with the secondary outcomes on immune function.

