7.2.2 Serious adverse events (SAEs)

In this study, the sponsor will report only the SAEs related to the exercise intervention, the blood sampling (T0 en T1) and the biopsy (T1). The sponsor will report these specific SAE's through the web portal *ToetsingOnline* to the accredited METC that approved the protocol, within 7 days of first knowledge for SAEs that result in death or are life threatening followed by a period of maximum of 8 days to complete the initial preliminary report. All other SAEs will be reported within a period of maximum 15 days after the sponsor has first knowledge of the serious adverse events.

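### Recorded adverse events give no fair comparison between arms, and post-randomisation toxicity, treatment and hospitalisation are classed as covariates with no by-arm comparison specified

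*Protocol*

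**What the plan says.** **Adverse events.** Protocol section 7.2.1 first defines an AE as any unwanted experience during the study, "whether or not considered related to the experimental intervention". It then says that what will be recorded for this study is "all exercise-related AE's and AE's related to the biopsy (T1) and blood sampling" at T0 and T1, whether the patient volunteers it or staff observe it. Section 7.2.2 applies the same limit to expedited reporting: "the sponsor will report only the SAEs related to the exercise intervention, the blood sampling (T0 en T1) and the biopsy (T1").

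**Exposure.** Randomisation follows the baseline assessment (6.2). Controls keep to their usual activity and are offered the programme only once the T1 biopsy has been taken (section 5.1, usual care group).

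**Clinical data.** Section 6.1.3 lists "disease, treatment and treatment-related toxicity" and hospitalisation among the clinical data, below a heading on demographic and clinical covariates. Section 6.3 takes them from medical records at baseline and during and/or after the intervention, with no restriction by arm. Table 1 schedules disease, treatment and toxicity at T0 and T1.

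**Analysis.** Section 8.3 states: "Descriptive statistics are calculated for covariates (smoking, sociodemographics and clinical data"). Section 8.2 specifies between-arm analyses of immune markers, physical fitness and quality of life.

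**The concern.** Two features combine.

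First, the recording rule keeps an event only if someone links it to exercise or to a study procedure. The biopsy and the blood draws are common to both arms. Exercise is what was randomised, and before T1 essentially only one arm can produce an event of that kind. An event that exercise might make more frequent, but that is put down to chemotherapy, such as an admission or a delayed cycle, is not recorded as an AE.

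Second, the data that could answer the question are largely collected already but are given the wrong role. Toxicity, admissions and changes to chemotherapy after randomisation can be affected by the intervention. The protocol's own rationale says so: it cites chemotherapy completion and fewer dose adjustments as effects of exercise (sections 1, 5.1 and 9.3). They belong with the outcomes, not beside smoking and sociodemographics.

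At stake is whether this pilot, meant to prepare a larger trial, uses its randomised control group to describe tolerability. There is also a link to the primary endpoint. Low blood counts or infection at T1 rule out the second biopsy and such patients are not replaced (6.3, 6.5), so toxicity by arm would help explain where evaluable biopsies are lost.

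**Working it through.** The plan gives no figure on this point, so the main check is of the text.

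**Step 1. Which recorded AEs can arise in which arm, from allocation to T1**

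| Type of recorded AE | Exercise arm | Control arm |
|---|---|---|
| Related to study exercise | yes | essentially none; programme offered after the T1 biopsy |
| Related to T0 blood sampling | yes, drawn before allocation | yes, drawn before allocation |
| Related to T1 biopsy or T1 blood sampling | yes | yes |
| Put down to chemotherapy or anything else | not recorded as an AE | not recorded as an AE |

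The first row is the only one that bears on the randomised contrast, and it is filled for one arm.

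**Step 2. What the rule does when the true risks are equal (illustration; every rate is assumed)**

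The protocol gives N = 20 but no allocation ratio, so take 10 per arm. Let p be the true risk of any AE before T1, the same in both arms, and q the share of AEs in the exercise arm judged exercise-related. Expected patients with such a recorded AE in the exercise arm = 10 × p × q; in controls, about 0.

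- p = 0.3, q = 0.1: 10 × 0.3 × 0.1 = 0.3
- p = 0.6, q = 0.25: 10 × 0.6 × 0.25 = 1.5
- p = 0.9, q = 0.5: 10 × 0.9 × 0.5 = 4.5

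With no true difference, the recorded counts run from 0.3 to 4.5 patients against about 0. The gap reflects the recording rule, not harm.

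**Step 3. Role of the record-based data**

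- Collected: treatment, toxicity and hospitalisation, not restricted by arm (6.1.3, 6.3); treatment and toxicity at T0 and T1 (Table 1). Table 1 has no row for hospitalisation.
- Class: covariates in 8.3 and under the heading in 6.1.3, yet Table 1 places clinical data beneath its secondary outcome heading, which covers nearly everything. The labels do not agree.
- Between-arm analysis in section 8: immune markers, fitness and quality of life. None is stated for AEs, toxicity, hospitalisation or chemotherapy changes.

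**Step 4. What a by-arm table could show (10 per arm assumed)**

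- 3/10, exact (Clopper-Pearson) 95% interval: 6.7% to 65.2%.
- 0/10, two-sided 95% upper limit: 1 − 0.025^(1/10) = 30.8%.
- Power of a two-sided Fisher exact test at 5%: about 13% for 20% versus 50%, and about 43% for 20% versus 70%.

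These figures support description and rule out a useful test.

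**The case against.** The strongest reply is that this is a feasibility pilot. Its success criteria are recruitment and evaluable biopsies. It calls the safety of the exercise programme well documented, and section 7.2.1 narrows a general definition openly, for this study. Descriptive statistics for clinical data are already promised, and whether a table has a column per arm is usually settled in a statistical analysis plan. With about 10 patients per arm the table could separate little.

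Much of this stands, and it rules out several stronger readings that a reader might infer:

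- **That the safety data will never be compared by arm.** Section 8.3 says neither pooled nor by arm. Only the absence of a specified comparison can be stated.
- **That the trial can report only a one-arm list of events.** Biopsy and blood-sampling AEs apply to both arms, QLQ-C30 is completed in both, and quality of life is compared.
- **That the record-based data are free of attribution.** Toxicity is limited to treatment-related toxicity, which itself needs a judgement.
- **That hospitalisation is scheduled at T1.** Table 1 does not list it, and section 6.3 leaves the time window loose.
- **That relatedness is judged by a named unblinded assessor.** Section 6.2 says "The pathologist and analyst that will examine the blood and biopsy tissue will be blinded to group allocation" and "The researcher that examines the physical fitness will not be blinded to group allocation", but names no one for relatedness. Knowledge of the arm is a fair inference, since an exercise-related judgement needs it, but it is not stated.
- **That a model adjusts for post-randomisation variables.** None in section 8.2 does; the linear models adjust for baseline values.

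The reply does not reach two things. The recording rule governs data collection, and no later analysis plan can recover AEs that were never recorded. And section 8.3 does assign these data a role, which is wrong for values measured after randomisation.

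**Conclusion.** The point holds as a cheap improvement, not as a flaw that invalidates a result. Followed as written, the AE rule yields no fair comparison of the randomised contrast before T1, and section 8 does not commit to comparing toxicity, hospitalisation or chemotherapy changes by arm, although it classes them as covariates when after randomisation they are outcomes. No figure in the protocol changes, and the two feasibility criteria are untouched.

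The textual part rests on sections 5.1, 6.1.3, 6.3, 7.2.1, 8.2 and 8.3 alone. The precision figures assume 10 patients per arm; the illustration of the recording rule also assumes its rates.

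**What to change.** 1. **Section 8.3 (and the heading in 6.1.3).** Limit covariates to baseline values. Tabulate post-baseline toxicity, all hospitalisations and chemotherapy changes from T0 to T1 by randomised arm, whether or not attributed to exercise, as numbers of patients with exact intervals. Label the table descriptive, with no test.
2. **Section 6.3 and Table 1.** State that hospitalisation is extracted for the same T0 to T1 window in both arms, so that the table can be filled.
3. **Section 7.2.1.** Reconcile the AE definition with the recording rule. If recording stays restricted, say so in the definition, and state that counts of exercise-related AEs are not a comparison between arms.

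Reporting to the METC under 7.2.2 is unchanged.

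**Cost.** One descriptive table from records that are largely collected already, and a few sentences of protocol text. The downside is that counts from about 10 patients per arm may be over-read; the label and the wide intervals guard against that.

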9. ETHICAL CONSIDERATIONS

9.1 Regulation statement

The study will be conducted according to the principles of the Declaration of Helsinki (version, date, see for the most recent version: www.wma.net) and in accordance with the Medical Research Involving Human Subjects Act (WMO).

9.2 Recruitment and consent

The patients will be recruited and informed about the study by the treating physician or nurse from the patient's own hospital. They will receive the patient information in which the study is outlined and the practical implication of study participation will be explained. Patients are asked if the study coordinator is allowed to make a call to the patient to further explain the study. The study coordinator will call the patients to answer any remaining questions and to set up a first appointment if they want to participate in the study. Since time between diagnosis of breast cancer and start of chemotherapy is short, patients will have two days to consider their decision for participation in this study. All patients will sign an IC statement prior to participation in the study. Patients will be recruited from the department of Medical Oncology from the Amsterdam UMC and 2 other sites.

9.3 Benefits and risks assessment, group relatedness

Patients randomized to the exercise group will be guided by a physical therapist that is educated specifically on the exercise protocol for this study and is used to working with oncology patients. The safety of the exercise intervention has well been documented and the program meets the American College of Sports Medicine's exercise recommendations for patients with cancer [17].

Therefore, we expect a negligible risk for participants with regard to the exercises. In addition, evidence from randomized controlled trials, including our own, shows that exercise during cancer treatment benefits physical fitness, fatigue and quality of life [4, 5].

Additionally, women with breast cancer who exercised during chemotherapy appeared to have fewer dose adjustments[3]. For this reason, the control group will be offered the same intervention after 6 weeks. Even though this evidence exists, referral to a physical therapist during chemotherapy is not standard care because costs for physical therapy are not covered with basic insurance.

The risks of the blood drawing and fitness test are negligible. The patients that perform one of their exercise sessions in the VUmc (to be able to collect blood samples for IL-6 monitoring) will be guided by an experienced physical therapist. In case of emergency during this specific training, the emergency procedure of the department of rehabilitation medicine will be followed.

The risk of clinically relevant complications of a breast biopsy was around 0,2% in a multi-institutional study in 1994 [8]. Nowadays, the risk of complications is even lower, due to technological improvements that are implemented. The biopsies are very important to study the effect of an exercise intervention on infiltration of immune cells in the tumor.

9.4 Compensation for injury

The sponsor/investigator has a liability insurance which is in accordance with article 7 of the WMO.

The sponsor (also) has an insurance which is in accordance with the legal requirements in the Netherlands (Article 7 WMO). This insurance provides cover for damage to research subjects through injury or death caused by the study.

The insurance applies to the damage that becomes apparent during the study or within 4 years after the end of the study.

9.5 Incentives (if applicable)

Patients will receive compensation for their travel costs for the measurements.

10. ADMINISTRATIVE ASPECTS, MONITORING AND PUBLICATION

10.1 Handling and storage of data and documents

All data and human material will be handled confidentially and treated coded. All subjects will receive an unique code and only the investigators will know the key to this code. The coded data are stored in a digital database on an intern network, which is protected by a password that only the investigators have access to. The handling of personal data should comply with the EU General Data Protection Regulation and the Dutch Act on Implementation of the General Data Protection Regulation.

The data will be stored for a period of 15 years. The biopsy material will be stored and analyzed at the biobank unit of the pathology department. The blood samples will be stored and analyzed in the department of clinical chemistry and partly in the Cancer Center Amsterdam. The human material will be used for immune monitoring during this trial and will be destroyed when the analyses for this trial are completed and the manuscript has been published (if applicable).

The human material will not be exchanged with other countries.

10.2 Monitoring and Quality Assurance

From the risk classification of our study we determined a negligible risk and therefore the use of a certified data monitor is not necessary. Data monitoring will be performed the Clinical Research Bureau of our institute. He or she will compare the data entered into the database with the hospital or clinic records (source documents). The nature and location of all source documents will be identified to ensure that all sources of original data required to complete the database are known to the investigational staff and are accessible for verification. At a minimum, source documentation must be available to substantiate: subject identification, eligibility and participation; proper informed consent procedures; data of visits; adherence to protocol procedures; records of safety and efficacy parameters; adequate reporting and follow-up of adverse events; date of subject completion, discontinuation from treatment, or

Direct access to source documentation (medical records) must be allowed for the purpose of verifying that the data recorded in the database are consistent with the original source data.

10.3 Amendments

Amendments are changes made to the research after a favorable opinion by the accredited METC has been given. All amendments will be notified to the METC that gave a favorable opinion.

10.4 Annual progress report

The sponsor/investigator will submit a summary of the progress of the trial to the accredited METC once a year. Information will be provided on the start of the study, date of inclusion of the first subject, numbers of subjects included and numbers of subjects that have completed the trial, serious adverse events/ serious adverse reactions, other problems, and amendments.

10.5 Temporary halt and (prematurely) end of study report

The investigator/sponsor will notify the accredited METC of the end of the study within a period of 8 weeks. The end of the study is defined as the last patient's last visit.

The sponsor will notify the METC immediately of a temporary halt of the study, including the reason of such an action.

In case the study is ended prematurely, the sponsor will notify the accredited METC within 15 days, including the reasons for the premature termination.

Within one year after the end of the study, the investigator/sponsor will submit a final study report with the results of the study, including any publications/abstracts of the study, to the accredited METC.

